#### 2.3 Exploratory

- Assess circulating tumor DNA (ctDNA) as a potential treatment response tool.
- Correlate clinical data, outcomes and toxicity with biomarkers of EZH2 inhibition and resistance - potentially including but not limited to circulating or tumor molecular profiling, epigenetics, and immune system activity.

### 3. STUDY DESIGN

#### 3.1 Study Overview

This is a single institution, open label, single-arm phase 2 trial. We plan to accrue up to 50 subjects in order to meet our goal of 29 evaluable subjects. Each subject will be administered Tazemetostat orally twice daily for subjects with recurrent and/or metastatic MPNST. Subjects will be dosed in continuous 28 day cycles, and as follows:

- Pediatric (12y- <18y): 520 mg/m^2/dose orally BID, not to exceed 800 mg orally twice daily
- Adult: ( $\geq 18$ y): 800 mg orally BID (flat dose for adults)

Surveillance imaging of primary and metastatic sites will be performed every 2 cycles, +/- 7 days after Cycle 1 Day 1, until disease progression or death. ctDNA testing results will be collected whenever performed per standard of care.

Response to treatment will be evaluated via RECIST 1.1. Treatment with Tazemetostat will continue until disease progression, unacceptable toxicity or withdrawal of consent or termination of study. Screening data will be reviewed to determine subject eligibility. Subjects who meet all inclusion criteria and none of the exclusion criteria will be entered into the study.

Total duration of subject participation will be 24 months. Total duration of the study is expected to be 36 months.

#### 4. SELECTION OF SUBJECTS

Subjects with a clinical diagnosis of recurrent and/or metastatic MPNST who meet the following inclusion and exclusion criteria at study enrollment will be eligible for participation in this study. **Per UFHCC guidelines, exceptions to inclusion and exclusion criteria are not permitted.** For questions concerning eligibility, please contact the PMO ([[contact]](mailto:[contact])).

##### 4.1 Number of Subjects

Up to 50 people will be enrolled in this study to achieve 29 evaluable subjects.

##### 4.2 Inclusion Criteria

Individuals eligible for study participation must meet the following criteria at enrollment:

- A. A histologic confirmation of recurrent/refractory and/or metastatic MPNST with RECIST measurable disease.
- B. Subjects  $\geq 12$  years of age at the time of enrollment
- C. Performance status:
  - 12-15 years old- Lansky  $> 50$
  - 16-17 years old- Karnofsky  $> 50$
  - $\geq 18$  years old- ECOG score 0-2
- D. Subjects must have adequately recovered from the acute toxic effects of all prior anti-cancer therapy per enrolling physician and must meet the following minimum duration from prior anti-cancer directed therapy prior to enrollment. Subjects who have not received any anti-cancer treatment prior to study treatment are also eligible to enroll.
  - Anti-cancer agents known to be Myelosuppressive:  $\geq 28$  days after the last dose of agent.
  - Anti-cancer agents not known to be myelosuppressive:  $\geq 7$  days after the last dose of agent.
  - Antibodies:  $\geq 21$  days must have elapsed from infusion of last dose of antibody, and toxicity related to prior antibody therapy must be recovered to Grade  $\leq 1$ .
  - Systemic Corticosteroids: if related to prior therapy  $\geq 14$  days must have elapsed, or on stable dose for treatment of CNS disease.
  - Hematopoietic growth factors:  $\geq 14$  days after the last dose of a long-acting growth factor.

- Interleukins, Interferons, and Cytokines (other than hematopoietic growth factors):  $\geq$  21 days after the completion of interleukins, interferon or cytokines (other than hematopoietic growth factors).
- XRT/External Beam Irradiation including Protons:  $\geq$  14 days after local XRT;  $\geq$  150 days after TBI, craniospinal XRT or if radiation to  $\geq$  50% of the pelvis;  $\geq$  42 days if other substantial BM radiation.
- Radiopharmaceutical therapy:  $\geq$  42 days after systemically administered radiopharmaceutical therapy.
- Major surgery  $\geq$  14 days prior, with evidence of wound healing and no active surgical complications

E. Subjects must not have had prior exposure to Tazemetostat or other inhibitor(s) of EZH2.

F. Adequate laboratory values of organ function, defined as:

- Peripheral absolute neutrophil count (ANC)  $\geq$  1000/mm^3.
- Platelet count  $\geq$  100,000/mm^2 (transfusion independent, defined as not receiving platelet transfusions for at least 7 days prior to enrollment).
- Hemoglobin  $\geq$  8.0 g/dL at baseline (may receive RBC transfusions).
- Creatinine clearance or radioisotope GFR  $\geq$  70 ml/min/1.73 m^2, or serum creatinine based on age/gender as followed in Appendix H.
- Total bilirubin  $\leq$  1.5 ULN or direct bilirubin  $\leq$  1 x ULN.
- Aspartate aminotransferase (AST) and alanine aminotransferase (ALT)  $\leq$  2.5 x ULN; if liver metastases present, then AST and ALT must be  $\leq$  5 x ULN.
- Serum albumin  $\geq$  2 g/dL.
- Coagulation INR  $\leq$  1.5, while on anti-coagulation INR  $\leq$  2.5.

G. Nervous system disorders (CTCAE v5.0) resulting from prior therapy must be  $\leq$  Grade 2, with the exception of decreased tendon reflex (DTR). Any grade of DTR is eligible.

H. Subjects must not have more than one active malignancy at the time of enrollment (Subjects with a prior or concurrent malignancy whose natural history or treatment does not have the potential to interfere with the safety or efficacy assessment of the investigational regimen [as determined by the treating physician and approved by the PI] may be included).

I. Written informed consent obtained from the subject and the subject agrees to comply with all the study-related procedures. All subjects and/or their parents or legally authorized representatives must sign a written informed consent. Assent, when appropriate, will be obtained according to institutional standard practice.

J. Use of contraception:

- Women of childbearing potential (WOCBP) who are heterosexually active must be using two highly effective methods of contraception to avoid pregnancy throughout the study and for at least 6 months after the last dose of study drug to minimize the risk of pregnancy as Tazemetostat might counteract the effects of hormonal contraceptives. Birth control methods that can be used while in this study include: established use of oral, injected or implanted hormonal birth control or placement of an intrauterine device [IUD] or intrauterine system [IUS]. They or their partner must also use a second method, (e.g., condom with spermicidal foam/gel/film/cream/suppository or occlusive cap [diaphragm or cervical/vault caps] with spermicidal foam/gel/film/cream/suppository. If their male partner is vasectomized, they do not need to use any of the birth control methods listed above. The type of birth control they use must be discussed with the study doctor before beginning the study. The study doctor must approve the method you use before they can enter the study. Prior to study enrollment, women of childbearing potential must be advised of the importance of avoiding pregnancy during trial participation and the potential risk factors for an unintentional pregnancy.
- Males with female partners of child-bearing potential must agree to use physician-approved contraceptive methods (e.g., abstinence, condoms, vasectomy) throughout the study and should avoid donating sperm, for 90 days following the last dose of study drug.

#### 4.3 Exclusion Criteria

Subjects with any of the following present at time of enrollment will not be eligible for study participation:

- A. Subjects who are currently taking the following concomitant medications:
  - Anti-cancer Agents: Subjects who are currently receiving other anti-cancer agents are not eligible.
  - CYP3A4 Agents: Subjects who are currently receiving drugs that are strong inducers or strong inhibitors of CYP3A4 are not eligible. Strong inducers or inhibitors of CYP3A4 are prohibited from 14 days prior to the first dose of Tazemetostat to the end of the study. Note: Dexamethasone for CNS tumors or metastases, on a stable dose, is allowed.
  - Grapefruit, grapefruit juice, Seville oranges and food/drinks containing them should be avoided one week before the first dose of the study intervention
- B. Subjects who are acutely ill with an uncontrolled active infection on systemic anti-infective agents are not eligible.

- C. Subjects with a prior history of T-LBL/T-ALL, myelodysplastic syndrome (MDS), acute myeloid leukemia (AML), B-cell acute lymphoblastic leukemia (B-ALL), or other myeloproliferative neoplasm (MPN).
- D. Subjects who have any of the following underlying major cardiac issues or conditions:
  - Known QTc prolongation or documentation
  - Documented New York Heart Association (NYHA) Class III or IV congestive heart failure.
  - Myocardial infarction within 6 months prior to registration.
  - Unstable angina within 6 months prior to registration.
  - Symptomatic arrhythmia.
- E. Subjects who in the opinion of the investigator may be high risk for treatment complications or unable to comply with the safety monitoring requirements of the study are not eligible.
- F. Heterosexually active males or females of reproductive potential may not participate unless they have agreed to use two highly effective contraceptive methods for the duration of study treatment as Tazemetostat might counteract the effects of hormonal contraceptives. Female subjects of childbearing potential should agree to remain abstinent or use adequate contraceptive methods for 6 months after the last dose of Tazemetostat. Male subjects should agree to remain abstinent or use adequate contraceptive methods, and agree to refrain from donating sperm, and for 90 days after the last dose of Tazemetostat.
- G. Females who are pregnant or breastfeeding will not be entered on this study because there is currently no available information regarding human fetal or teratogenic toxicities. Pregnancy tests must be obtained in girls who are post-menarchal.
- H. Administration of a vaccine containing live virus within 30 days prior to the first dose of trial treatment. For examples, See Section 7.3.3: Prohibited Concomitant Therapy. **Note:** Most flu vaccines are killed viruses, with the exception of the intra-nasal vainer (Flu-Mist) which is an attenuated live virus and therefore prohibited for 30 days prior to first dose. Patients may receive non-live versions of the COVID-19 vaccine.
- I. Prisoners or subjects who are involuntarily incarcerated, or subjects who are compulsorily detained for treatment of either a psychiatric or physical illness.

- J. Known hypersensitivity to tazemetostat or any component of the formulation of tazemetostat
- K. Inability to take oral medication OR have malabsorption syndrome or any other uncontrolled gastrointestinal condition (eg, nausea, diarrhea, vomiting) that might impair the bioavailability of tazemetostat

#### 4.4 Inclusion of Women and Minorities

Any subjects who meet eligibility criteria may enroll in this trial.

### 5. REGISTRATION PROCEDURES

All consented subjects must be entered into the University of Florida's Clinical Trial Management System (OnCore) prior to assignment of a subject identification number. The study team must submit the completed study specific eligibility checklist, supporting source documentation and a copy of the signed informed consent document(s) to the UFHCC Project Management Office (PMO; [[contact]](mailto:[contact])) or their assigned Project Manager. Upon receipt of a completed eligibility packet, the designated Project Manager will review the source to verify eligibility and assign a subject number. No subject may be enrolled until his/her eligibility packet is complete and eligibility is verified by PMO. If eligibility cannot be confirmed, the project manager will query the site for clarification or additional documents as needed. Subjects failing to meet all study eligibility requirements will not be able to participate in the trial.

All eligible and enrolled subjects will receive a unique subject number. This number will be used to identify the subject throughout the study. Subjects withdrawn from the study will retain their subject number.

### 6. STUDY PROCEDURES

Written informed consent must be obtained prior to performing any study-specific evaluations or tests. Tests or evaluations performed as standard of care within the specified screening period, but prior to informed consent, may be accepted for this study and need not be repeated. All clinical and laboratory studies to determine eligibility must be performed within 7 days prior to enrollment unless otherwise indicated in Section 6.2. Laboratory tests need **not** be repeated at the baseline visit (C1D1) if therapy starts **within 72 hours** of obtaining screening labs to assess eligibility. If a post-enrollment lab value is outside the limits of eligibility, then the following laboratory evaluations must be re-checked within 48 hours prior to initiating therapy: CBC with differential, bilirubin, ALT (SGPT) and serum creatinine. If

UF-SC-001

2024-Aug-12

the recheck is outside the limits of eligibility, the patient may not receive protocol therapy and will be considered off protocol therapy. Imaging studies must be obtained within 30 days prior to start of protocol therapy.

## 6.1 Schedule of Events

Procedure:	Visit:	SCREENING (Windows outlined in Section 6.2)	CYCLE 1	CYCLES 2 AND BEYOND (WITHIN 72 HRS PRIOR)	END OF TREATMENT (WITHIN 14 DAYS OF LAST STUDY DRUG ADMINISTRATION)	FOLLOW UP (28 +/- 7 DAYS AFTER LAST DOSE OF TREATMENT)	SURVIVAL FOLLOW UP EVERY 90 +/- 14 DAYS AFTER LAST DOSE
Informed Consent		X					
Medical History, Demographic Information		X					
Clinical Exam		X	X	X	X		
Performance status (PS) 		X	X	X	X		
Vital Signs (VS) including height  , weight, and BSA 		X	X	X	X		
Numbered Pain Rating Scale 			X	X	X		
Labs (CBC diff, CMP) 		X	WEEKLY 	X			X 
Pregnancy Test (Urine or Serum) 		X	X	X			
INR		X					
Tibial x-ray 		X		X 			
Provide Study Drug for home administration			X	X			
Tumor disease evaluation 		X		EVERY 2 CYCLES 	X		
Tumor NGS 		X					
Circulating tumor DNA (ctDNA) 				X	X		
Provide and/or Review Subject Diary			X	X	X		
Concomitant Medication Review 		X	X	X	X		
Adverse Event Review 			X	X	X	X	
Survival Assessment							X

Abbreviations: VS=vital signs (blood pressure, temperature, pulse and respiratory rates, weight and height); CBC/diff=complete blood count and white blood cell differential; CMP = complete metabolic profile (sodium, potassium, chloride, bicarbonate, blood urea nitrogen, creatinine, glucose, alkaline phosphatase, AST, ALT, total bilirubin, protein), NGS Next Generation Sequencing

1 Performance status: Pediatric Karnofsky for subjects  $\geq$  16 years of age and Lansky for subjects 12-15 years of age; Adult ECOG score (18+)

UF-SC-001

2024-Aug-12

- 2 Numbered Pain Rating Scale , refer to Appendix G.
- 3 Laboratory tests at baseline need not be repeated if therapy starts within 72 hours of obtaining labs to assess eligibility. Labs are to be collected weekly for Cycle 1 (Days 1, 8, 15, and 22) +/- 72 hours. If patients have Grade 4 neutropenia then CBCs should be checked at least every other day until recovery to Grade 3 or until meeting the criteria for dose limiting toxicity. Automated differentials acceptable unless concern for blasts; then please obtain manual differential.
- 4 Female subjects of childbearing potential only.
- 5 Patients must have either CT or MRI of primary and metastatic tumors, as well as whole body 18F-FDG PET/CT. Radiographic Tumor Assessment using RECIST 1.1 criteria. Imaging to be obtained every 2 cycles +/- 7 days from Cycle 1 Day 1 until disease progression or death. Screening imaging studies must be obtained within 30 days prior to start of protocol therapy.
- 6 Tumor NGS will be sent as part of standard of care, if not already done. If already done, results will be recorded as part of medical history review.
- 7 Circulating tumor DNA (ctDNA) results will be collected whenever obtained per standard of care.
- 8 Height and BSA only collected for pediatric subjects.
- 9 Adverse events, comed collection, and all sample collections, should be performed pre-dose at every cycle. The study drug will be provided at study visits, but self-administered at home throughout the trial. Cycles may be repeated for up to a total duration of therapy of 2 years (maximum 26 cycles), provided the patient meets the criteria for starting subsequent cycles and does not meet any of the criteria for removal from protocol therapy criteria.
- 10 Only to be completed for subjects <18 years of age. Screening tibial x-ray may have been performed within the past 6 months (180 days) before treatment (C1D1).
- 11 Tibial x-rays to be completed every 180 +/- 30 days only for those with open growth plates at screening.
- 12 CBC only – at each survival follow-up visit for five years, then yearly (at least once per calendar year) up to 10 years. Once a subject begins new anti-cancer therapy, they will be followed for survival only.

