Inclusion Criteria:	
Individuals eligible for study participation must meet the following criteria at enrollment:
 
A. A histologic confirmation of recurrent/refractory and/or metastatic MPNST with RECIST measurable disease.
 
B. Subjects <math>\geq</math> 12 years of age at the time of enrollment.
 
C. Performance status:
 
 
• 12-15 years old- Lansky > 50
 
• 16-17 years old- Karnofsky > 50
 
• <math>\geq</math>18 years old- ECOG score 0-2
 
 
D. Subjects must have adequately recovered from the acute toxic effects of all prior anti-cancer therapy per enrolling physician and must meet the following minimum duration from prior anti-cancer directed therapy prior to enrollment.
 
 
• Anti-cancer agents known to be Myelosuppressive: <math>\geq</math> 28 days after the last dose of agent.
 
• Anti-cancer agents not known to be myelosuppressive: <math>\geq</math> 7 days after the last dose of agent.
 
• Antibodies: <math>\geq</math> 21 days must have elapsed from infusion of last dose of antibody, and toxicity related to prior antibody therapy must be recovered to Grade <math>\leq</math> 1.
 
• Systemic Corticosteroids: if related to prior therapy <math>\geq</math> 14 days must have elapsed, or on stable dose for treatment of CNS disease.
 

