#### 7.5.3 Prohibited Concomitant Therapy

Supportive care measures consistent with optimal subject care will be permitted throughout the study, as long as the therapy is not included in this section as prohibited.

Subjects are prohibited from receiving the following therapies during the Screening and Treatment Phase of this trial:

- Concurrent cancer therapy, including chemotherapy, radiation therapy, immunotherapy, or biologic therapy may NOT be administered to patients receiving study drug. If these treatments are administered the patient will be removed from protocol therapy.
- Investigational agents other than the study drug in this trial.
- Radiation therapy (allowed if  $\geq$  14 days prior to study registration).
- Cancer-Related Surgery (allowed if  $\geq$  14 days prior to study registration).
- Strong inhibitors and inducers of CYP2C8, CYP2D6, and P-glycoprotein (P-gp) should be used with caution.
- Medications that are sensitive or narrow therapeutic range substrates of CYP3A, CYP2C8, CYP2C9, CYP2C19, CYP2D6 should be avoided if possible. Other substrates of CYP2C8, 2C9, 2C19, 2D6, 3A, P-gp, OATP1B1, OATP1B3, OAT3, MATE1, and MATE2K should be used with caution.
- CYP3A4/5 inhibitors or inducers: Strong CYP3A4/5 inhibitors or inducers are prohibited from 14 days prior to the first dose of Tazemetostat to the end of the study (Appendix F). Note: Dexamethasone for CNS tumors or metastases, on a stable dose, is allowed.
- Live vaccines within 30 days prior to the first dose of trial treatment and while participating in the trial. Examples of live vaccines include, but are not limited to, the following: measles, mumps, rubella, chicken pox, yellow fever, rabies, BCG, and typhoid (oral) vaccine. Seasonal influenza vaccines for injection are generally killed virus vaccines and are allowed. However, intranasal influenza vaccines (e.g. Flu - Mist®) are live attenuated vaccines, and are not allowed. Patients may receive non-live versions of the COVID-19 vaccine.

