### Lesions with Prior Local Treatment:

- Tumor lesions situated at a previously irradiated area, or in an area subjected to other loco-regional therapy, are non-measurable unless there has been demonstrated progression in the lesion.

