## **Specifications by Methods of Measurement**

All measurements should be recorded in metric notation, using a ruler or calipers if clinically assessed. All baseline evaluations should be performed as closely as possible to

the beginning of treatment and never more than 4 weeks before the beginning of the treatment. The same method of assessment and the same technique should be used to characterize each identified and reported lesion at baseline and during follow-up. Imaging-based evaluation should always be done rather than clinical examination unless the lesion(s) being followed cannot be imaged but are assessed by clinical exam.

An adequate volume of a suitable contrast agent should be given so that the metastases are demonstrated to best effect and a consistent method is used on subsequent examinations for any given subject. If prior to enrollment it is known a subject is not able to undergo CT scans with intravenous contrast due to allergy or renal insufficiency, the decision as to whether a non-contrast.

CT or MRI (with or without intravenous contrast) should be used to evaluate the subject at baseline and follow-up should be guided by the tumor type under investigation and the anatomic location of the disease.

*Clinical Lesions:* Clinical lesions will be considered measurable only when they are superficial and  $\geq 10$  mm diameter as assessed using calipers (for example, skin nodules). For the case of skin lesions, documentation by color photography, including a ruler to estimate the size of the lesion is recommended. When lesions can be evaluated by both clinical exam and imaging, imaging evaluation should be undertaken since it is more objective and may be reviewed at the end of the study.

*Chest X-ray:* Chest CT is preferred over chest X-ray when progression is an important endpoint. Lesions on chest X-ray may be considered measurable if they are clearly defined and surrounded by aerated lung.

*CT and MRI:* CT scan is the best currently available and reproducible method to measure lesions selected for response assessment. Measurability of lesions on CT scan is based on the assumption that CT slice thickness is  $\leq 5$  mm. When CT scans have slice thickness  $> 5$  mm, the minimum size for a measurable lesion should be twice the slice thickness. MRI is also acceptable in certain situations (for example, for body scans). If there is concern about radiation exposure at CT, MRI may be used instead of CT in selected instances.

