### Frequency of Tumor Re-Evaluation

A baseline tumor evaluation must be performed within 4 weeks before a subject begins study treatment. Frequency of tumor re-evaluation while on and adapted to treatment should be protocol-specific and adapted to the type and schedule of treatment. Normally, all target and non-target sites are evaluated at each assessment using the same method. However, bone scans may need to be repeated only when CR is identified in target disease or when progression in bone is suspected.

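### The baseline RECIST scan is not required to follow the last prior anti-cancer treatment, so a change in tumor size caused before C1D1 can enter the primary ORR

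*Combined protocol and SAP*

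**What the plan says.** **Scan timing.** Section 6, Section 6.1 (footnote 5) and Section 6.2 all allow 30 days: "Screening imaging studies must be obtained within 30 days prior to start of protocol therapy". Appendix C sets a different limit in two places: "never more than 4 weeks before the beginning of the treatment" (Specifications by Methods of Measurement) and "A baseline tumor evaluation must be performed within 4 weeks before a subject begins study treatment" (Frequency of Tumor Re-Evaluation). Section 6 also admits scans done before consent: "Tests or evaluations performed as standard of care within the specified screening period, but prior to informed consent, may be accepted for this study".

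**Washouts.** Inclusion criterion D (Synopsis and Section 4.2) counts back from enrollment. For "Anti-cancer agents not known to be myelosuppressive" the minimum is "7 days after the last dose of agent". It is 14 days for local radiotherapy and for major surgery, 21 for antibodies and for cytokines, and 28 for myelosuppressive agents.

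**Therapy during screening.** Section 7.5.3 bars other cancer therapy during screening and treatment, but excepts earlier radiotherapy and surgery ("Cancer-Related Surgery (allowed if" at least 14 days before registration).

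**Locally treated lesions.** Under Appendix C, lesions in irradiated or loco-regionally treated areas "are non-measurable unless there has been demonstrated progression in the lesion".

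**Use of the scan.** Appendix C defines PR as a fall of at least 30% from the baseline sum of diameters. PD is measured from the smallest sum on study, which can be the baseline sum. Best overall response is computed from investigator assessments. Appendix C mentions confirmation, but the protocol sets no confirmation requirement.

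**The concern.** The scan has one clock (days before C1D1) and the washouts have another (days before enrollment). A site can follow every sentence and still hold a baseline scan that predates the subject's last dose, fraction or operation. The first on-study assessment, after two cycles, is then compared with tumor measurements taken before that treatment had acted.

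If the earlier treatment shrinks the tumor, the fall is scored as a tazemetostat response in ORR and CBR. If the tumor grows between the scan and C1D1, the growth is scored as progression on drug. A single-arm, open-label trial has no comparator in which either error would show. The stage 1 rule turns on 3 responses in 9 subjects and the final rule on 10 in 29, so single misattributed responses matter.

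**Working it through.** **1. The plan's own design figures.** Inputs from Section 12.2: null ORR 21%, alternative 45%, stop if 2 or fewer of 9 respond, reject if 10 or more of 29 respond. With X1 ~ Bin(9, p) and X2 ~ Bin(20, p):

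P(continue) = P(X1 ≥ 3)

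P(reject) = Σ over x = 3 to 9 of P(X1 = x) × P(X2 ≥ 10 − x)

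- p = 0.21: P(continue) = 1 − (0.1199 + 0.2867 + 0.3049) = 0.289; P(reject) = 0.0485.
- p = 0.45: P(reject) = 0.804.

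The stated 5% and 80% are reproduced.

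**2. How far the scan may precede the last prior treatment.** Ceiling = max(0, scan window − washout − e), where e is the number of days from enrollment to C1D1. The documents give no value for e; e = 0 gives the maximum.

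| Prior treatment | Washout (days) | 30-day window | 4-week window |
|---|---|---|---|
| Non-myelosuppressive agent | 7 | 30 − 7 = 23 | 28 − 7 = 21 |
| Local radiotherapy | 14 | 30 − 14 = 16 | 28 − 14 = 14 |
| Major surgery | 14 | 16 | 14 |
| Antibody | 21 | 30 − 21 = 9 | 28 − 21 = 7 |
| Interleukin, interferon, cytokine | 21 | 9 | 7 |
| Myelosuppressive agent | 28 | 30 − 28 = 2 | 0 |
| Other substantial marrow radiation, radiopharmaceutical | 42 | 0 | 0 |
| TBI, craniospinal or large pelvic field | 150 | 0 | 0 |

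Each day of enrollment-to-C1D1 delay removes one day. Section 4.2 also admits previously untreated subjects, for whom the question does not arise. Moving from 30 days to 4 weeks takes off at most two days, so settling that conflict would not close the gap.

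**3. One carried-over response in stage 1 (assumed to have occurred).** One of the nine counts as a response whatever the drug does, so two more are needed among eight.

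- p = 0.21: P(continue) = P(Bin(8, 0.21) ≥ 2) = 1 − (0.1517 + 0.3226) = 0.526, against 0.289. P(reject) = 0.099, against 0.0485.
- p = 0.10 (assumed): P(continue) rises from 0.053 to 0.187. P(reject) stays at or below 0.001.

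**4. A share c of non-responders carried over (assumed range).** The apparent response rate is p + (1 − p)c, put into the formula of step 1.

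| c | True ORR 21%: apparent rate | P(reject) | True ORR 10%: apparent rate | P(reject) |
|---|---|---|---|---|
| 0 | 0.210 | 0.0485 | 0.100 | 0.0002 |
| 3% | 0.234 | 0.088 | 0.127 | 0.002 |
| 5% | 0.250 | 0.124 | 0.145 | 0.004 |
| 10% | 0.289 | 0.244 | 0.190 | 0.026 |

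Neither c nor the true ORR can be read from the documents. The table also models shrinkage only, not growth before C1D1.

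**The case against.** **Locally treated lesions are largely covered.** The tempting example is a lesion irradiated or resected about 15 days before C1D1 and then scored as a response. Appendix C classifies lesions at baseline, and Sections 6 and 7.1 call C1D1 the baseline visit. If the rule is applied with information up to C1D1, an area irradiated two weeks earlier counts as previously irradiated and its lesion leaves the target sum. Resection is arguably loco-regional therapy as well. Measurable disease must also be present at enrollment. This stands for the most part. What is left is the exception for demonstrated progression. It is not tied to progression after the local therapy, so a lesion that progressed, was then irradiated and is now shrinking could remain a target.

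**Drugs are barred during screening.** Section 7.5.3 does bar them, and its 14-day allowance applies only to radiotherapy and surgery. The 23-day and 9-day figures therefore need a standard-of-care scan, then further drug, and only then the start of screening. That narrows the route without closing it. The protocol does not define when screening starts, and Section 6.2 allows consent at any time in the 28 days before C1D1. The 7-day washout itself contemplates drug given well inside the scan window.

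**Appendix C asks for baseline evaluation as close as possible to treatment start.** That is a general aim. It does not order the scan relative to prior therapy.

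**The direction is open.** Section 1.1 describes an aggressive tumor, so growth before C1D1 is as plausible as late shrinkage. This stands.

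**Conclusion.** The gap in the text is established: nothing requires the baseline scan to follow the last prior treatment, and PR is measured from that scan. It is clearest for systemic agents given after a standard-of-care scan but before screening begins. For locally treated lesions there is a partial safeguard. For myelosuppressive chemotherapy the gap is at most 2 days, and zero under the 4-week rule. All the day counts are ceilings.

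A reader might infer that the ORR will be inflated, or that the type I error is really 10% or 24%. The documents support neither. They give no frequency of exposed subjects, and error can run both ways. The 9.9% is conditional on a carried-over response having occurred. The 24.4% needs a 10% carry-over share and a true ORR of exactly 21%, a figure that Section 1.2 takes from chemotherapy in chemo-naive patients. At an assumed true ORR of 10%, the same shares give 0.2%, 0.4% and 2.6%. These figures show only that the decision rule is sensitive to single responses.

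The point is worth making because the bias would fall on the primary endpoint of an uncontrolled trial and is cheap to exclude. The conflict between 30 days and 4 weeks is a separate, smaller error that rests on no assumption: a scan on day −29 or −30 satisfies Section 6 and breaches Appendix C.

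**What to change.** 1. In Section 6, Section 6.1 footnote 5 and Section 6.2, state that the baseline RECIST scan is obtained after the last dose or fraction of any prior anti-cancer therapy and after any tumor surgery. A scan followed by such treatment may not serve as baseline.
2. In Appendix C, Lesions with Prior Local Treatment, state that the progression meant is progression after the local therapy.
3. Separately, reconcile the 30-day window in Sections 6, 6.1 and 6.2 with the 4-week limit in Appendix C, so that one limit applies throughout.

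With the first change, the overlap in the first table is zero days for every class of prior treatment. The washout periods, N = 29 and both decision rules stay unchanged, so alpha (0.0485) and power (0.804) do too. The cost is a short amendment and, for a few subjects, a baseline scan taken later in the window or an older standard-of-care scan replaced.
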